9.3. Statistical Analysis

- 9.3.1. For each subject's position detection, INVSENSOR00011 output will be compared against observer's notes at each turn of the subject.
- 9.3.2. Correctly detected position changes will be marked as True Positive.
- 9.3.3. Missed detections (if any) will be counted.
- 9.3.4. Combining the two, sensitivity of INVSENSOR00011's posture change detection will be computed as Sensitivity = True Positive/(True Positive + Missed Detection)
- 9.3.5. From the INVSENSOR00011's output, all false positives will be counted, i.e., when a turn is indicated by INVSENSOR00011 but the observer's notes do not agree with that. These will present a measure of specificity of the device.
- 9.3.6. Heart rate readings from INVSENSOR00011 will be compared against reference pulse-rates to compute mean and standard deviation of the differences.
- 9.3.7. Respiration rate readings from INVSENSOR00011 will be compared against reference respiration rate to compute mean and standard deviation of the differences.

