1. PURPOSE

The objective of this study is to assess INVSENSOR00011's clinical performance for detection of a subject's position and posture in bed, subject's activity (sitting, standing, etc.) [REDACTED] and respiratory rate. Only noninvasive sensors and corresponding devices will be employed to collect data from healthy volunteers in this study.

This is a nonrandomized single arm study where all of the subjects are enrolled into the experimental arm and will receive the INVSENSOR00011 device on their chest or back, along with a RAM (Rainbow Acoustic Monitoring) sensor on their neck, a pulse oximeter on their finger, and a nasal cannula which will be attached to the capnography device.

Outcome Measure: Assess the clinical performance of the detection of position, posture and activity through comparing INVSENSOR00011 measurements to observer's notes. Assess INVSENSOR00011's [REDACTED] respiratory rate measurements through comparison with those from [REDACTED] RAM.

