9. SAMPLE SIZE JUSTIFICATION AND DATA ANALYSIS PROCEDURE TO BE USED

9.1. Sample Size Determination

In each subject, the protocol induces at least five position changes during the study. To assess INVSENSOR00011's detection capability, the device output will be compared against observer's notes for each change. Assuming a sample size $N = 30$, there will be at least 150 independent data points collected, which will be used for validation. This data will be enough for calculating sensitivity and specificity of the position detection algorithm.

9.2. For heart rate and respiration rate comparison, the study does not have an accuracy requirement to meet. However, INVSENSOR00011's heart rate and respiration rate measurements will be compared against reference measurements for an assessment. $N=30$ is deemed sufficient for a qualitative assessment of performance.

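### Section 9.3 yields one unstratified sensitivity and a false-positive count without a denominator, so it gives no calculable specificity and no separate result for activity

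*Combined protocol and SAP*

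**What the plan says.** Section 1 (Purpose) names three things to detect: position, posture in bed, and "subject's activity (sitting, standing, etc".). Its outcome measure is to "Assess the clinical performance of the detection of position, posture and activity" by comparing the device with observer's notes.

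Section 9.1 plans 30 subjects with at least five induced position changes each. It says that "the device output will be compared against observer's notes for each change" and concludes: "This data will be enough for calculating sensitivity and specificity of the position detection algorithm".

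Section 9.3 then sets out the analysis:

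- 9.3.1 compares device and notes at each turn.
- 9.3.2: "Correctly detected position changes will be marked as True Positive".
- 9.3.3: "Missed detections (if any) will be counted".
- 9.3.4: "sensitivity of INVSENSOR00011's posture change detection will be computed as Sensitivity = True Positive/(True Positive + Missed Detection").
- 9.3.5 counts turns that the device indicates and the notes do not support, and adds: "These will present a measure of specificity of the device".
- 9.3.6 and 9.3.7 cover heart rate and respiration rate only.

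Items 9.3.1 to 9.3.7 run in sequence with no redaction mark. The procedure in 7.5.1 to 7.5.3 is redacted. Section 8 states that there are no acceptance criteria, and a redaction follows.

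**The concern.** The stated outcome is wider than the analysis. Activity does not appear in Section 9.3. Nothing there separates one position or posture from another, and the specificity that 9.1 treats as calculable is replaced by a count.

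With no visible acceptance threshold, the figures from 9.3 are the visible answer to the position, posture and activity outcome, so they need to be interpretable on their own. Section 2.1 justifies the device by its ability to tell staff which position a patient is in, and describes position parameters being combined over time into a pressure-injury risk. A device that fails in one position but does well elsewhere would matter for that use, and a single rate would not show it. A false-positive count with no time or opportunity beside it cannot be compared with any other device or study.

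**Working it through.** **1. The plan's own figure.** 30 subjects × 5 changes = 150, which matches the minimum in 9.1. The documents give no target rate, precision or error rates, so every count below other than 30, 5 and 150 is assumed for illustration.

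**2. Outcome against analysis.**

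| Stated in Section 1 or 9.1 | Supplied by 9.3.1 to 9.3.5 |
|---|---|
| Detection of position and posture | One sensitivity formula for posture change, no strata |
| Detection of activity | Not mentioned; at most merged with turns in bed |
| Sensitivity | TP/(TP + missed), with a missed detection left undefined |
| Specificity | Count of false-positive turns, no true negatives, no denominator |

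**3. Specificity.** Specificity = TN/(TN + FP) = 1 − FP/(opportunities for a false turn). Take FP = 10 and vary the number of opportunities, which 9.3.5 does not define:

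- 30 opportunities: 1 − 10/30 = 66.7%
- 150: 1 − 10/150 = 93.3%
- 900: 1 − 10/900 = 98.9%
- 1800: 1 − 10/1800 = 99.4%

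The same count fits anything from 66.7% to 99.4%.

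**4. What one rate can hide.** Assume the 150 changes form 5 classes of 30, with 5 changes not flagged (one per class) and 15 flagged with the wrong position. Correct = 150 − 5 − 15 = 130. Count wrong-position turns as failures:

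- Overall: 130/150 = 86.7%.
- Wrong positions spread evenly (3 per class): (30 − 1 − 3)/30 = 26/30 = 86.7% in every class.
- All 15 in one class: (30 − 1 − 15)/30 = 14/30 = 46.7% there (95% Wilson 30% to 64%), and 29/30 = 96.7% in each of the other four. Check: 14 + 4 × 29 = 130.

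The overall figure is the same in both cases. Other counts make the same point: four classes at 30/30 and one at 15/30 give 135/150 = 90.0% overall, with 50% in the failing class.

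**5. The 9.3.4 denominator.** 9.3.2 read with 9.1 most naturally makes a wrong-position turn a failure, as in step 4. If such turns were treated as neither correct nor missed, they would leave the denominator: 130/(130 + 5) = 130/135 = 96.3% overall, and 14/(14 + 1) = 14/15 = 93.3% in the poor class.

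**6. What a per-class table adds, and what it does not.** If all 15 wrong calls went to one other class, that class's one-versus-rest specificity at noted changes would be (120 − 15)/120 = 105/120 = 87.5% (95% Wilson 80% to 92%, ignoring clustering within subject). This measures confusion between positions. It leaves out every false turn flagged when no change was noted, so it does not replace the 9.3.5 quantity.

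**7. Precision per class.** With an assumed 30 events per class, 27/30 = 90% has a 95% Wilson interval of 74% to 97%.

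**The case against.** The strongest case on the other side has five parts.

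- **No result per position is promised.** Section 9.1 speaks of one algorithm, and Section 1 puts the three detections in a single outcome sentence. A reader might infer that 9.3 breaks a commitment to per-position estimates. The documents contain no such commitment, so this part of the point is an improvement and not an inconsistency.
- **Activity may already be scored.** A reader might infer that activity is not analysed at all. The visible text cannot show that: 7.5.1 to 7.5.3 are redacted, and Section 13.4 says subjects get out of bed, so sit or stand transitions may be among the scored changes. What stands is narrower. Section 9.3 is unredacted and would merge such transitions with turns in bed.
- **Pooling is inferred.** 9.3.1 opens with each subject's detection, and 9.3.4 does not say results are combined. Pooling is the most natural reading of a single formula. A per-subject calculation would still not separate positions or activities.
- **A false-positive count is a reasonable summary for events in a continuous signal**, where true negatives have no natural count. This is fair, and it argues for a rate over time. It does not turn a bare count into the specificity that 9.1 says can be calculated.
- **The illustration is hypothetical.** It is. Section 9.1 does not say the five changes are five distinct classes, and the error counts are assumed. The figures show what the analysis could not reveal, not what the device will do.

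A reader might also infer that 9.3.4 inflates sensitivity by dropping wrong-position turns. That needs the less natural reading of 9.3.2, so it is a wording risk and not a demonstrated bias.

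**Conclusion.** The point holds in limited form. On the visible text, 9.3.1 to 9.3.5 cannot produce the specificity that 9.1 says the data support, and they give no separate activity result. The unstratified sensitivity can conceal failure in one position: with the assumed counts, 86.7% overall is compatible with 46.7% in one class. The missing denominator does not depend on the redacted text. Whether activity is scored at all does.

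This is a cheap improvement. No visible pass/fail decision changes, since Section 8 shows no acceptance criteria. It would also be wrong to infer that one-versus-rest specificity from a cross-tabulation fills the gap in 9.3.5, because it is calculated only at changes the observer noted.

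**What to change.** 1. **9.3.4:** use all observer-noted changes as the denominator, and count a change as detected only when the device's new position matches the notes.
2. **9.3.5:** report false turns flagged when no change was noted as a rate per recorded hour. Report turns flagged with the wrong position separately. Do not call the bare count a specificity.
3. **New item in 9.3:** add a descriptive device-by-observer cross-tabulation of the noted positions, postures and activities, including sitting and standing where scored, with a column for changes not flagged. Give sensitivity per class, and one-versus-rest specificity labelled as confusion between positions at noted changes.

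**Cost.** A few words in 9.3 and one table from a comparison already planned, with no added subjects or procedures. Reported sensitivity may fall. Per-class figures will be imprecise (step 7) and should be presented as descriptive. Section 7.5.5 refers to a set of steps, so the intended position at each step should be known. If neither those steps nor the case report form carries a position label, the form needs one more field.

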7.5. Study Procedure

- 7.5.1. Apply sensors. [REDACTED]

- 7.5.2. [REDACTED]

- 7.5.3. [REDACTED]

[REDACTED]	[REDACTED]	[REDACTED]

[REDACTED]	[REDACTED]	[REDACTED]
[REDACTED]	[REDACTED]	[REDACTED]
[REDACTED]	[REDACTED]	[REDACTED]

7.5.4. [REDACTED] All enrolled subjects will be paid [REDACTED] after the completion of the study with no additional compensation for travel. Subjects who do not complete the study will be paid [REDACTED] with no additional compensation for travel.

7.5.5. In case of an error in following the instruction set, subject can repeat the missed steps.

7.5.6. Subjects may stop the study at any time.

7.5.7. Data collected in this study may be used in the future for product development, publications, and/or submissions to the FDA or other regulatory agencies.

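### The 150 induced position changes are all reference-positive as scored, so they cannot give the specificity that section 9.1 promises; section 9.3.5 yields only a count of false turns

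*Combined protocol and SAP*

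**What the plan says.** Section 9.1 (Sample Size Determination) makes the induced position change the data point. There are at least five per subject and 30 subjects, hence at least 150, each checked against the observer's notes. It concludes: "This data will be enough for calculating sensitivity and specificity of the position detection algorithm".

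Section 9.3 (Statistical Analysis) sets the scoring:

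- 9.3.1 fixes the occasion of comparison: "INVSENSOR00011 output will be compared against observer's notes at each turn of the subject".
- 9.3.2 defines the successes: "Correctly detected position changes will be marked as True Positive". 9.3.3 counts the misses, and 9.3.4 divides the first by the sum of the two to give sensitivity.
- 9.3.5 turns to the device output: "all false positives will be counted, i.e., when a turn is indicated by INVSENSOR00011" without support in the notes. Of these counts it says: "These will present a measure of specificity of the device".

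A formula is written out for sensitivity. None is given for specificity.

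**The concern.** Specificity is the proportion of reference-negative units that the device correctly leaves unflagged. It needs a set of occasions on which the observer recorded no turn. An induced change is by construction an occasion on which a turn took place, so a sample made up of induced changes carries no information on specificity, however large it is. Section 9.1 therefore claims a property that the data, as scored in 9.3, do not have.

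Section 9.3.5 does capture false turns, but a count cannot be interpreted without the time, or the number of intervals, over which it arose. If the denominator is chosen after the data are seen, the reported specificity depends on that choice.

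The error in question is relevant to the intended use. Section 2.1 presents the device as a means of ensuring that patients are repositioned, and a falsely indicated turn could suggest a repositioning that did not happen. Section 7.5.7 allows the data to go into publications and regulatory submissions, where a specificity without a denominator could not be assessed.

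**Working it through.** **The plan's own figure.** 30 subjects × 5 changes = 150, as section 9.1 states. It is a minimum, but further induced changes would also be reference-positive.

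**Where the 150 go.** By 9.3.2 to 9.3.4, sensitivity = TP/(TP + missed), and TP + missed = 150. Reference negatives among the 150 = 150 − 150 = 0. Specificity = TN/(TN + FP) has no denominator from these points.

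**Whether the count in 9.3.5 can stand in.** The documents give neither a false-turn count nor a number of negative units, so this is an illustration and not an estimate for this trial. Assumed inputs: 10 false turns, each in its own window; 30 or 60 minutes per subject; windows of 10 seconds or 1 minute.

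Windows = 30 × minutes × 60 / window length in seconds. Specificity = (windows − 10)/windows, with and without removal of the 150 windows that contain an induced change.

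| Session | Window | All windows | Specificity | After removing 150 | Specificity |
|---|---|---|---|---|---|
| 30 min | 10 s | 5,400 | 99.81% | 5,250 | 99.81% |
| 30 min | 60 s | 900 | 98.89% | 750 | 98.67% |
| 60 min | 10 s | 10,800 | 99.91% | 10,650 | 99.91% |
| 60 min | 60 s | 1,800 | 99.44% | 1,650 | 99.39% |

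With the change windows removed, 1 minus specificity runs from 10/750 = 1.33% down to 10/10,650 = 0.09%, a ratio of 10,650/750 = 14.2, from the same 10 false turns.

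With fewer and coarser negative units the spread is wider. Ten false positives among an assumed 30 units give 20/30 = 66.7% (exact 95% CI 47.2% to 82.7%); among 150, 140/150 = 93.3% (88.1% to 96.8%); among 900, 890/900 = 98.9% (98.0% to 99.5%).

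**The same count as a rate.** 30 subjects × 30 min = 15 h, and 10/15 = 0.67 per hour (exact Poisson 95% CI 0.32 to 1.23). 30 subjects × 60 min = 30 h, and 10/30 = 0.33 per hour (0.16 to 0.61). These intervals make no allowance for clustering by subject. The rate needs a defined monitored time but no window length.

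**The alternative reading.** If the device were scored on which position it reports, each point would be a negative for every class other than its own. With 4 or 5 equally used classes (assumed), that gives 150 × 3/4 = 112.5 or 150 × 4/5 = 120 negatives per class.

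**The case against.** Four points deserve an answer.

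- **The plan takes false positives from the whole device output, not from the 150 scored turns.** On this view the negatives were never meant to lie among the 150, and the real gap is an unstated denominator. That is fair to 9.3.5. But 9.1 attributes the sufficiency for specificity to the change data, and the missing denominator is itself the defect.
- **Section 7.5 is largely redacted and may define still periods or a session length.** Section 5.2 excludes people who cannot sit still or keep movement minimal for at least 30 minutes, which suggests that such time is part of the session. This stands as far as it goes: a time base may well be recoverable. But 9.1 and 9.3 show no redaction and use no such period.
- **The plan may mean classification of position.** The outcome in section 1 is worded "Assess the clinical performance of the detection of position, posture and activity through comparing INVSENSOR00011 measurements to observer's notes", and 9.1 and 9.3.1 also speak of position detection. Under that reading the points could serve as negatives for other classes. But 9.3 names no classes, 9.3.4 computes the sensitivity of detecting a posture change, and 9.3.5 defines a false positive as an indicated turn. If classification is meant, the text has to say so.
- **Little depends on it.** No visible acceptance criterion exists (the rest of the line in section 8 is redacted), 9.3.5 promises only a measure, and the illustration rests on assumed inputs. All true, and this limits the consequence to a result that cannot be interpreted. It does not make the count a specificity, and 9.1 speaks of calculating one.

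**Conclusion.** The concern holds. Following 9.3 as written gives a sensitivity on at least 150 points and an unscaled count of false turns. It does not give the specificity that 9.1 says the data will support.

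The part that rests on the documents alone is 150 reference-positive points, no negatives among them, and no denominator or time base stated. The numerical spread in specificity rests on assumed counts, session lengths and windows; it shows only that the count does not determine the figure. Sensitivity is unaffected, no visible pass/fail decision is at risk, and a denominator can still be fixed before analysis. It should be corrected, because the result would otherwise carry a label that it does not earn.

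**What to change.** In 9.1, state that the induced changes, as scored in 9.3, support the estimate of sensitivity. In 9.3.5, replace the sentence on specificity with one of these:

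1. **A rate.** Report false turn detections per hour of monitored time with a 95% CI that allows for clustering by subject. Define monitored time, including whether the turns themselves count and how repeated steps are handled, since 7.5.5 provides: "In case of an error in following the instruction set, subject can repeat the missed steps". Note that the rate applies to the scripted session.
2. **A specificity.** Fix a negative unit before analysis, for example no-change intervals of set length taken from the observer's notes, and compute TN/(TN + FP).

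If the sponsor means classification of position, 9.3 should say so, list the classes and define specificity per class.

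The cost is wording in two sections, one definition and one tabulation from the same sessions, provided that session times and the timing of turns are recorded. The reported figure may look less favourable than a specificity based on short windows.

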9.4. Expected Dropout Rates

Subjects may not complete the study for various reasons, such as a clinical screening test failure, at the Principal Investigator's discretion, or because the subject does not want to continue the study. Expected dropout rate for this study is approximately 0% of the total number of subjects enrolled.

10. ADVERSE EVENTS

Definitions:

Adverse event: Any untoward medical occurrence in a subjects, users or other persons, whether or not related to the medical device under study.

Device-related adverse event: Adverse event related to, associated with, or caused by, the use of a medical device under study, including but not limited to events that may have been attributed to the device because of device failure or malfunction, improper or inadequate design, manufacture or user error.

Device deficiency: Inadequacy of a medical device with respect to its identity, quality, durability, reliability, safety or performance. Device deficiencies include malfunctions, use errors and inadequate labeling.

If there is a device deficiency during the study, it will be documented on the Case Report Form, [REDACTED] and it will be reported according to department procedures.

Serious adverse event: Adverse event that: a) led to death, b) led to serious deterioration in the health of the subject, that resulted in: (i) a life-threatening illness or injury, (ii) a persistent or significant impairment of a body structure or a body function, (iii) in-patient or prolonged hospitalization, or (iv) medical or surgical intervention to prevent life-threatening illness or injury or permanent impairment to a body structure or a body function, or c) led to fetal distress, fetal death or a congenital abnormality or birth defect. NOTE: Planned hospitalization for a pre-existing condition, or a procedure required by the clinical investigational plan, without serious deterioration in health, is not considered a serious adverse event.

10.1 Adverse Events

All devices used in the study are non-significant risk devices. All study procedures are noninvasive. In the unlikely event that an adverse event should occur, it will be reported and documented as described below.

All adverse events that occur during the study shall be recorded on the Case Report Form. The Adverse Event Form [REDACTED] shall also be completed.

Skin irritation or redness from the adhesive are anticipated adverse events.

10.2 Serious and Unanticipated Adverse Events

The investigator shall promptly report to the IRB within 24 hours any serious and unanticipated adverse event involving subjects.

At the time of discharge from the study, an unresolved serious and unanticipated adverse event(s) will be followed up by the investigator until the event(s) are resolved, stabilized, or the patient is unable to follow-up or the adverse event is otherwise explained. The investigator will also instruct the subject to report any subsequent events occurring in the next 30 days, which the subject or the subject's physician believes might reasonably be regarded as caused by or have a reasonable possibility of being caused by the test device or procedures involved in the study.

10.3 Unanticipated Problems

Any unanticipated problems involving subjects will be reported to the IRB, such as protocol violations or deviations as required by the IRB reporting procedures.

11. SUPPORTING DOCUMENTATION AND OPERATIONAL CONSIDERATIONS

11.1. Measures Taken to Protect the Rights and Welfare of Subjects

11.1.1 All subjects will be monitored closely throughout the study.

11.1.2 The following measures will be taken to insure the privacy of the subjects:

11.1.2.1 Information about the patients will be kept confidential.

11.1.2.2 An identification number (code) for each subject will be kept on file.

11.1.2.3 The study documents will only contain the subject's corresponding identification number except in the Informed Consent Document.

11.1.2.4 Access to identifying documents and data will only be granted to the investigators in the study.

11.1.2.5 Study data that will be released to Masimo and other regulatory authorities will be de-identified and will only pertain to study data collection, demographics, sensor placement locations and recordings from devices.

11.1.2.6 The confidentiality and retention of these documents will be protected to the extent provided and required by the law.

